1.2. Schema

1.3. Schedule of Activities

The SoA table provides an overview of the protocol visits and procedures. Refer to the **STUDY ASSESSMENTS AND PROCEDURES** section of the protocol for detailed information on each procedure and assessment required for compliance with the protocol.

The investigator may schedule visits (unplanned visits) in addition to those listed in the SoA table, in order to conduct evaluations or assessments required to protect the well-being of the participant.

References to “baseline” in this study correspond to the Week 24 visit of the Phase 2 C0251002 study and Day 1 of this study. All study procedures will be completed for Visit 24 in the C0251002 study, and Day 1 in the current study prior to drug administration.

Table 1. DM Participants with Moderate to Severe Skin Disease

This SoA focuses on DM participants with moderate skin disease including participants from Amended Stage 2 of the Phase 2 C0251002 study. The approximate study duration is 68 weeks; 48 weeks of study treatment, (treatment period is up through and including Week 52) with a 16 week follow up period.

Protocol Activity	Treatment Period														Follow-up ^s				
	1 Baseline	2	3	4	5	6	7	8	9	10	11	12	13	14	15	16	17	18	Participant withdrawal or Early Termination ^a
Visit identifier (Study Visit)	Week 24 C0251002 DAY 1	Week 4	Week 8	Week 12	Week 16	Week 20	Week 24	Week 28	Week 32	Week 36	Week 40	Week 44	Week 48	Week 52	Week 56	Week 60	Week 64	Week 68	N/A
Study Day/Week																			
Visit Window	(+/-) 7 days*	±3 days																	
Informed consent	X																		
Inclusion/exclusion criteria ^b	X																		
Medical history ^c	X																		
Demography	X																		
Clinical Reported Outcomes																			
C-SSRS ^d	D			X			X			X			X			X		X	X
PhGA VAS ^e	D			X			X			X			X	X		X		X	X
CDASI	D			X			X			X			X	X		X		X	X

Protocol Activity	Treatment Period														Follow-up ^s				
	1 Baseline	2	3	4	5	6	7	8	9	10	11	12	13	14	15	16	17	18 EOS	Participant withdrawal or Early Termination ^a
Visit identifier (Study Visit)	Week 24 C0251002 DAY 1	Week 4	Week 8	Week 12	Week 16	Week 20	Week 24	Week 28	Week 32	Week 36	Week 40	Week 44	Week 48	Week 52	Week 56	Week 60	Week 64	Week 68	N/A
Visit Window	(+/-) 7 days*	±3 days																	
Patient Reported Outcomes																			
SF36 v2 Acute ^f	D			X			X			X				X			X		X
EQ-5D-5L & EQ-VAS ^f	X			X			X			X				X			X		X
Medical Assessments																			

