2.2.1.1.4. Efficacy and Safety (Phase 2 C0251002 Study, Stage 1)

C0251002 is an ongoing multi-center, double blind randomized placebo-controlled Phase 2 study to evaluate the efficacy, safety, tolerability and PK of PF-06823859 in adult patients with active DM. Stage 1 of the study was designed to evaluate the effects of 600 mg PF-06823859 and placebo administered IV at baseline, Week 4 and Week 8 in participants with skin-predominant DM. The data summarized below are a high level summary based upon a snapshot date of 27 February 2020. In that the database of this study is not yet final, this should be considered preliminary evidence.

The primary endpoint of Stage 1 of the study was the change from baseline in the CDASI-A score at Week 12. A clinically and statistically significant difference in CDASI-A score over time was observed between the active and placebo treatment arms. The least squares mean difference estimate of CFB in the CDASI-A in the active treatment versus the placebo group (primary endpoint) was -14.82 (90% CI -20.26, -9.37, $p=0.0001$).

A 13-gene Type 1 IFN gene signature was used to assess pharmacodynamic activity in skin biopsies. The % change from baseline levels of the gene signature at Week 12 on lesional skin was markedly lower (83.6%) for the PF-06823859 group compared to the placebo group (11.8%), showing pharmacodynamic activity (one sided $p=0.00016$).

PF-06823859 at a dose of 600 mg IV was generally safe and well tolerated, with a comparable safety profile between the PF-06823859 and placebo groups. No deaths occurred in Stage 1 of the Phase 2 study. There were 3 SAEs and 2 permanent discontinuations due to TEAEs, all of which were considered unrelated to treatment by both investigator and Sponsor. Most TEAEs were mild or moderate in severity and occurred at a similar frequency in the active treatment and placebo groups. Based on the preliminary estimates of effect from the Stage 1 data of Study C0251002, PF-06823859 demonstrates a favorable benefit-risk profile in the potential treatment of DM.

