3. OBJECTIVES, ENDPOINTS, AND ESTIMANDS

Objectives	Endpoints	Estimands
Primary: 
To evaluate the long-term safety and tolerability of PF-06823859.	Primary: 
Incidence of AEs, laboratory abnormalities, changes in vital signs, and ECG findings.	Primary: 
There are no defined estimands for safety and tolerability endpoints; these will be analyzed using Pfizer data standards, as applicable.
Secondary: 
To evaluate the long-term efficacy of PF-06823859 in adult participants with moderate to severe DM.	Secondary: 
Change from baseline in CDASI activity score at Week 52.Absolute values and change from baseline of CDASI activity and CDASI damage scores at all scheduled timepoints.TIS score at Week 52 and at intermediate scheduled timepoints for participants who	Secondary: 
E1: This estimand uses a hypothetical estimand strategy (ICH E9 addendum) estimating the mean effect of PF-06823859 in the absence of intercurrent events (study withdrawal). This is the mean change from baseline to Week 52 CDASI activity score for all randomized and dosed participants with non-missing baseline score in the (a) Skin Analysis Set and (b) Muscle Analysis Set (see details in Section 9.1.1).These additional CDASI endpoints will be analyzed using E1 at all scheduled timepoints.E2: This estimand uses a hypothetical estimand strategy (ICH E9 addendum) estimating the mean effect of PF-06823859 in the absence of intercurrent events (study

	
entered from Stage 3 of Protocol C0251002.
 
Change from baseline in the CSMs of the TIS including PhGA, PtGA, MMT-8, HAQ-DI, muscle enzymes, and MDAAT at Week 52 and at intermediate scheduled timepoints.	
withdrawal). This is the mean TIS at Week 52 for all randomized and dosed participants included with non-missing baseline score in the Muscle Analysis Set (see details in Section 9.1.1).
 
The endpoints for the CSM of the TIS will be analyzed using E2 at Week 52 and all intermediate scheduled timepoints.
Tertiary/Exploratory:	Tertiary/Exploratory:	Tertiary/Exploratory:

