- If there are “yes” answers on items 4, 5, or on any behavior question of the C-SSRS, the participant will be discontinued from treatment and referred to a mental health professional for appropriate evaluation and treatment (if the participant cannot be seen by a mental health professional within 24 hours, then the participant should be sent to a local emergency room for psychiatric assessment);
- All of the following laboratory abnormalities require discontinuation if they are confirmed (confirmation through re-testing is expected to occur within 1 week):
 - Two sequential AST or ALT elevation ≥ 3 times the upper limit of normal with at least one total bilirubin value ≥ 2 times the upper limit of normal;^a
 - Two sequential AST or ALT elevation ≥ 3 times the upper limit of normal accompanied by signs or symptoms consistent with hepatic injury;^a
 - Two sequential AST or ALT elevation ≥ 5 times the upper limit of normal, regardless of total bilirubin or accompanying signs or symptoms;^a

- Female participants found to be pregnant during the study;
- Other serious or severe AEs, after consultation with the Pfizer medical monitor or designee.
 - a. In each case, there is a need for additional investigations, such as review of ethanol, recreational drug and dietary supplement consumption; testing for acute hepatitis A, B or C infection and biliary tract imaging should be promptly discussed with the Pfizer medical monitor or designee.
- Use of prohibited medications require participant discontinuation as reflected in [Section 6.8.1](#) and [Appendix 8 \(Section 10.8\)](#) for prohibited medication listing.
- A participant who meets either bulleted criterion based on repeat ECG readings will be withdrawn from the study intervention.
 - QTcF >500 msec.
 - Change from baseline: QTcF >60 msec and QTcF >450 msec.

If a clinically significant finding is identified (including, but not limited to, changes from baseline in QTcF after enrollment), the investigator or qualified designee will determine if the participant can continue in the study and if any change in participant management is needed. This review of the ECG printed at the time of collection must be documented. Any new clinically relevant finding should be reported as an AE. See [Appendix 7 \(Section 10.7\)](#) for further details regarding ECG findings of potential clinical concern.

- Lack of efficacy will be the discretion of the investigator (see rescue medication guidance, [Section 6.8.4](#)).

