**Figure 1. Study Schema**

### **3. ENDPOINTS AND BASELINE VARIABLES: DEFINITIONS AND CONVENTIONS**

For the skin cohort (ie, participants entering C0251008 from Amended Stage 2 of C0251002), the major efficacy analyses assess changes in the modified CDASI *activity* and *damage* scores. The details of the calculation of these scores are presented in [Section 9.2](#).

For the muscle cohort (ie, participants entering C0251008 from Stage 3 of C0251002), the major efficacy analyses assess changes in the modified CDASI activity and damage scores and changes in the TIS and the CSM. The details of the calculation of the TIS are presented in [Section 9.3](#).

Safety assessments for the primary endpoint will be reported for all participants and by cohort. Efficacy assessments will generally be reported by cohort.

Unless specifically stated otherwise, the baseline value for all assessments is defined as the last non-missing measurement collected prior to the first administration of study drug at Day 1. Change from baseline is defined as the value at a specific visit minus the value from baseline.

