##### **3.1.2. Laboratory Abnormalities**

Reporting for laboratory data is described in [Section 6.6.2](#). To determine if there are any clinically significant laboratory abnormalities, the safety laboratory tests will be assessed against the criteria specified in the C0251008 Study Protocol. Baseline of safety laboratory tests will be the last pre-dose measurement.

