### **3.1.4. ECG Findings**

Reporting for ECG findings is described in [Section 6.6.4](#). Baseline will be the last measurement prior to receiving study treatment.

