##### Categories for QTcF

QTcF (msec)	450 < max. < 480	480 < max. < 500	max. > 500
QTcF (msec) increase from baseline	30 ≤ max. < 60	max. ≥ 60	

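### Safety change tables start at OLE Day 1, and the SAP does not define the parent-baseline safety analysis that the Protocol permits, so change that began on drug in the parent study is subtracted out

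*Protocol*

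**What the plan says.** The primary endpoint (Protocol 3) is "Incidence of AEs, laboratory abnormalities, changes in vital signs, and ECG findings".

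**Baseline.** In Protocol 1.3, references to baseline "correspond to the Week 24 visit of the Phase 2 C0251002 study and Day 1 of this study". In both schedule tables, Day 1 vital signs and ECG are marked as done at the parent Week 24 visit, while safety laboratory samples are collected under the OLE. SAP 3 sets the general rule as the "last non-missing measurement collected prior to the first administration of study drug at Day 1". SAP 3.1.2 adds "Baseline of safety laboratory tests will be the last pre-dose measurement". SAP 3.1.3 and 3.1.4 say, for vital signs and ECG, "Baseline will be the last measurement prior to receiving study treatment". Protocol 9.3.5.2 also fixes the ECG baseline at Day 1 before dosing.

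**Use of that baseline.** SAP 6.1.1, 6.6.3 and 6.6.4 summarise change from baseline. SAP 9.4 defines baseline-relative categories: "QTcF (msec) increase from baseline" (30 to below 60, and 60 or more), percentage increases in PR and QRS, and changes in systolic pressure of 30 mm Hg or more and in diastolic pressure of 20 mm Hg or more.

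**Parent-study baseline.** Protocol 1.1 and 9.3.1 permit sensitivity analyses from parent Day 1. Protocol 9.3.3 permits the same for longitudinal safety analyses, by name. All are optional, with details left to the SAP. In the SAP, 6.1.1.1 (sensitivity and supplementary analyses of the primary endpoint) has no text beneath it, 5.2 lists sensitivity analyses for efficacy scores only, and 6.4 plans no subset analyses.

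**Parent study.** Protocol 2.2.1.1.4 describes C0251002 as a "double blind randomized placebo-controlled Phase 2 study". Protocol 4.1 admits participants who complete its Week 24 visit during the treatment period.

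**The concern.** An extension study adds information on slow or cumulative effects. If the reference value was itself measured on drug, a change that arose in the parent study and persisted appears as no change, and a change that built up across both studies appears as its second part only. The participants affected are those with the longest exposure. Ex-placebo participants have a pre-drug Day 1, so the tables pool two different quantities without separating them.

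An optional analysis with no definition is also weak protection. Whether to run it, and with which rules, can be decided after the open-label data have been seen.

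**Working it through.** The plan states no figure on this point, so there is nothing to reproduce. The check has four steps.

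**1. Is Day 1 an on-drug value for ex-active participants?** Input: mean IV half-life of 23 to 29 days (Protocol 2.2.1.1.2, single doses). Assuming simple exponential decline, the fraction of a dose left after 28 days is 0.5^(28/t½).
- t½ = 23: 0.5^(28/23) = 0.43
- t½ = 29: 0.5^(28/29) = 0.51

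This assumes 4-weekly parent dosing with the last dose at Week 20, which the documents do not state. The only parent schedule given is that of Stage 1 (baseline, Weeks 4 and 8). Under that schedule, the sum of 0.5^((168 − d)/t½) over d = 0, 28 and 56 days gives 0.055 to 0.122 of one dose at Week 24. Since Week 24 lies within the treatment period for OLE entrants, the first case is the more natural reading, but it remains an inference.

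**2. Effect on a mean change.** Let p be the share from an active parent arm. Suppose the drug causes a shift d that had plateaued by parent Week 24 in ex-active participants and appears in full during the OLE in ex-placebo participants. The mean OLE change is then p × 0 + (1 − p) × d = (1 − p)d.

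| p (assumed) | Share of d shown |
|---|---|
| 0 | 100% |
| 0.5 (15 of 30) | 50% |
| 0.67 (20 of 30) | 33% |
| 1 | 0% |

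**3. Effect on category counts (assumed individual values).**

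| Measure | Parent Day 1 | OLE Day 1 | OLE visit | Change from OLE Day 1 | Change from parent Day 1 | Absolute class |
|---|---|---|---|---|---|---|
| Systolic BP | x | x + 20 | x + 40 | +20: no category | +40: in the ≥30 category | none for high values |
| QTcF, case A (msec) | 355 | 400 | 445 | +45: 30 to <60 | +90: ≥60 | none (below 450) |
| QTcF, case B (msec) | 400 | 435 | 462 | +27: no category | +62: ≥60 | 450 to 480 |

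**4. What do absolute limits recover?** SAP 9.4 has absolute classes for QTcF (450, 480, 500 msec), PR (≥300 msec), QRS (≥200 msec), low systolic (<90) and low diastolic (<50) pressure, and pulse. Case B is still seen through its absolute class. Case A is not. For blood pressure the absolute limits are on the low side only, so a rise is flagged solely by change from baseline. Mean-change summaries have no absolute counterpart that corrects for an on-drug baseline.

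**The case against.** The strongest reply is that the Protocol already provides for this: 9.3.3 names safety analyses with parent Day 1 as baseline. A reader might therefore infer that safety change can be counted only from OLE Day 1, and that inference would be wrong. What stands is narrower: the analysis is optional, was left to the SAP, and is not defined there.

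A reader might also infer that every parent-study shift disappears. The documents do not support that:
- Adverse event counts do not use this numeric baseline.
- Laboratory abnormalities are judged against protocol criteria (SAP 3.1.2).
- The absolute ECG and vital-sign classes remain.
- In case A the OLE rise is counted, in a lower class than the total warrants. With a total rise of 90 msec, the final QTcF stays at or below 450 only if parent Day 1 was 360 or lower.

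Entry rules limit what can be carried in. Protocol 5.2 screens haematology, liver tests and ECG, and excludes anyone who met parent discontinuation criteria or has an unresolved monitoring criterion. This removes large shifts. It does not remove smaller ones that continue to build, and the list has no specific blood-pressure limit.

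The parent study can assess its own shifts against placebo, and the OLE is descriptive. Both points lower the stakes. Neither gives the cumulative change across the two studies.

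Finally, a reader might extend the point to the discontinuation criteria in Protocol 10.10.2. No contradiction about baseline is shown there, and the change proposed here concerns tables only.

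**Conclusion.** The point holds for change measures. As the SAP is written, change summaries and baseline-relative categories for laboratory values, vital signs and ECG start at OLE Day 1, and no other safety baseline is specified. For participants from an active parent arm this understates cumulative change on drug. The gap is clearest for blood-pressure rises and mean changes, where absolute classes give no help, and partial for QTcF.

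The overall size cannot be fixed from the documents, because they do not give the active share, the allocation in Amended Stage 2 and Stage 3, or the timing of the last parent dose. Under the assumptions in the working, a plateaued shift would keep 50% of its size in the mean at p = 0.5 and 33% at p = 0.67. On-drug status at Day 1 is a sound inference from the design and the half-life, not a stated fact. This is a worthwhile, low-cost completion of the SAP and does not invalidate the planned tables.

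**What to change.** Under SAP 6.1.1.1, replace the bare heading with a commitment to a second set of laboratory, vital-sign and ECG change summaries and SAP 9.4 category counts. Define their baseline as the last value before the participant's first PF-06823859 dose in either study: parent Day 1 (pre-dose) for ex-active participants, OLE Day 1 for ex-placebo participants. Show the results by parent treatment, beside the OLE Day 1 tables, which stay as they are. Add a cross-reference in SAP 3.1.2 to 3.1.4 and 6.6.2 to 6.6.4.

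The cost is SAP wording, a merge of parent safety data and treatment codes once the parent study is unblinded, and duplicate descriptive tables. No visit, sample or procedure is added.

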2. INTRODUCTION

DM is an acquired rare inflammatory disease classified as both a neuromuscular disease and an autoimmune disease. DM is characterized by a distinctive skin rash and muscle weakness or inflamed muscles. Symptoms can come on suddenly or gradually over time. It is thought that the inflammation resulting in cell damage is created when the immune system attacks healthy muscle tissue and blood vessels under the skin. DM is idiopathic, however some individuals may have a genetic predisposition that is triggered by medications, viruses, bacteria, trauma, toxins, cancer or other illness. DM symptoms often wax and wane for no apparent reason, and females are affected twice as often as males.^{1,2}

2.1. Study Rationale

The purpose of the study is to evaluate the long-term safety, and tolerability of PF-06823859 in adult participants with DM who are eligible for enrollment from a qualifying study.

2.2. Background

DM has no known cure and there were no previously approved treatments prior to 2021 when IVIG, Octagam® 10% became the first approved treatment for adults with DM. However, complications of IVIG therapy have been well documented.³ Patients typically use a combination of drugs to seek relief for their inflammatory symptoms. Typically, the first line of treatment for the muscle disease is corticosteroids to address the inflammation as well as suppress the immune system. Other immunosuppressive drugs, notably azathioprine, methotrexate, MMF, and cyclophosphamide are used as subsequent lines of therapies in refractory cases or as steroid sparing agents. However, complications of long-term steroid and immunosuppressive therapies are also well documented. Other novel approaches have emerged as potential treatment, including tacrolimus (broadly immunosuppressive drug developed for transplant use), and rituximab, following positive outcomes in some case studies. However, additional randomized controlled trials with these treatments are needed to guide clinical practice.⁴ Consequently, DM remains a disease with very high unmet medical need, and development of safe and effective therapies is warranted.

PF-06823859 is a potent, selective, humanized IgG1 neutralizing antibody directed against the human soluble cytokine IFN β , a member of the type I IFN family of cytokines.

PF-06823859 is a novel compound in development for the treatment of DM with added potential for therapeutic benefit in SLE.

2.2.1. Clinical Overview

2.2.1.1. Safety (FIH C0251001)

A FIH study, C0251001, (Phase 1, Randomized, Double Blind, Third Party Open Placebo Controlled, Dose Escalating Study to Evaluate the Safety, Tolerability, Pharmacokinetics and Pharmacodynamics of Single and Multiple Intravenous and Subcutaneous Doses of PF-06823859 in Healthy adult Participants⁵) completed in August 2017. This study consisted of 8 dosing cohorts. There were 5 single dose cohorts 30 mg IV, 100 mg IV, 300 mg IV, 900 mg IV, and 2000 mg IV. The other 3 cohorts were multiple dose cohorts consisting of

100 mg x 3 SC doses (one dose every 2 weeks), 300 mg x 3 SC doses, (one dose every 2 weeks). The last cohort evaluated 2 dosing regimens due to a longer than expected half-life based on emerging data from the preceding cohorts. This last cohort consisted of 600 mg IV x 3 doses (one dose every 2 weeks) and 600 mg IV x 2 doses (one dose every 4 weeks).

A total of 62 participants completed the study; 48 participants were randomized to receive PF-06823859 and 14 participants were randomized to receive placebo. Results from this study suggest that PF-06823859 is generally well tolerated and safe when given up to 2000 mg as single dose and up to 600 mg administered IV every 2 weeks or every 4 weeks. The most common treatment-related TEAEs were somnolence, upper respiratory tract infection and headache. These adverse events were generally mild and resolved without further intervention. No serious AE or death occurred during the study.

One participant experienced an ISR after each of the 100 mg SC doses with PF-06823859 (3 doses) administered every 2 weeks. These were characterized by mild localized erythema with induration and tenderness, but no signs or symptoms of a systemic reaction. These local reactions resolved without further intervention within a few days. This participant also had treatment induced ADA, which had returned to baseline at the time of discharge ([Section 2.2.1.1.3](#); Immunogenicity Results).

Overall, there was no apparent difference in the total incidence of adverse events between participants treated with the active IP compared to placebo, and no apparent dose relationship with the incidence of AEs. However, the rate of mild upper respiratory tract infection appeared to be higher in participants treated with PF- 06823859.

There were no clinically significant changes in vital signs or laboratory abnormalities.

